11.7.4 Laboratory Test Results

Lab-defined lower and upper limits of normal ranges will be used for chemistry and hematology laboratory tests. NCI Common Toxicity Criteria (CTC) version 3.0 grading will be used. Laboratory results will be summarized with descriptive statistics at baseline and selected time points. Grade shifts in important laboratory results from baseline to worst on-protocol value will be presented. The incidence of post-baseline laboratory abnormalities will be provided.

11.7.5 Vital Signs

Descriptive analyses of temperature, blood pressure, and heart rate will be conducted at baseline and selected time points.

11.7.6 Exposure to Talimogene Laherparepvec

Summary statistics for exposure to talimogene laherparepvec, including total doses administered, total volume administered, duration from the first to the last administration of talimogene laherparepvec, and the average volume received by subject per visit will be provided and will be separated by the first (concentration of 10^6 PFU/ml) and subsequent doses (concentration of 10^8 PFU/ml). The subject incidence rate and reasons for IP delays, missed treatment, IP volume < 4 ml, and withdrawal will be tabulated.

11.7.7 Concomitant Medication, On-protocol Surgery or Procedure

Concomitant medications include all medications received during the treatment period other than the protocol drug. The number and proportion of subjects receiving any concomitant medications during the treatment period will be summarized by preferred terms as coded by the World Health Organization Drug (WHODRUG) dictionary.

Summary statistics for subjects in the Safety Analysis Set who undergo on-protocol surgery including any surgery/procedure performed, type of procedure, and intent of surgery (e.g., palliative) will be provided.

12. Changes From Protocol-specified Analyses

The following changes from the protocol are made in this document:

1. Remove the term “in injected and uninjected lesions” from the secondary objective: to explore the correlation between changes in an immunoprofile during treatment (in injected and uninjected lesions) and ORR, DRR, DOR, and changes in tumor burden. This revision is to avoid misleading.
2. The TTF definition is a modified definition of progression free survival (PFS). It is anticipated that we will change the endpoint from TTF to PFS in a future protocol amendment.

13. Literature Citations / References

- Kaplan and Meier. Nonparametric Estimation from Incomplete Observations
Journal of the American Statistical Association. 1958;53:457-481
- Brookmeyer, R. and Crowley, J. A Confidence Interval for the Median Survival Time. *Biometrics*. 1982;38:29–41.
- Kalbfleisch, J.D. and Prentice, R.L. *The Statistical Analysis of Failure Time Data*, New York: John Wiley & Sons. 1980
- Newcombe RG. Interval estimation for the difference between independent proportions: comparison of eleven methods. *Stat Med*. 1998;17:873-890.

14. Appendices

Appendix A. Conventions for Clinical Data That Require Imputation for Partial or Missing Date

The following data will be imputed using the following algorithm:

- Adverse Events and Deaths
- Concomitant Medications

Imputation Rules for Partial or Missing Start Dates

Start Date		Stop Date						
		Complete: yyyymmdd		Partial: yyyymm		Partial: yyyy		
		< 1 st dose	≥ 1 st dose	< 1 st dose yyyymm	≥ 1 st dose yyyymm	< 1 st dose yyyy	≥ 1 st dose yyyy	
Partial: yyyymm	= 1 st dose yyyymm	2	1	2	1	n/a	1	1
	≠ 1 st dose yyyymm		2		2	2	2	2
Partial: yyyy	= 1 st dose yyyy	3	1	3	1	n/a	1	1
	≠ 1 st dose yyyy		3		3	3	3	3
Missing		4	1	4	1	4	1	1

1 = Impute the date of first dose

2 = Impute the first of the month

3 = Impute January 1 of the year

4 = Impute January 1 of the stop year

Note: If the start date imputation leads to a start date that is after the stop date, then do not impute the start date.

Imputation rules for partial or missing stop dates:

- Initial imputation
 - a. For partial stop date mm-yyyy, impute the last of the month.
 - b. For partial stop date yyyy, impute December 31 of the year.
 - c. For completely missing stop date, do not impute.

- If the stop date imputation leads to a stop date that is after the death date, then impute the stop date as the death date.
- If the stop date imputation leads to a stop date that is before the start date, then set the stop date as missing.

Imputation rules for partial or missing death dates:

1. If death year and month are available but day is missing:
 - If mmYYYY for last contact date where subjects are known to be alive
= mmYYYY for death date, set death date to the day after the last contact date.
 - If mmYYYY for last contact date where subjects are known to be alive
< mmYYYY for death date, set death date to the first day of the death month.
 - If mmYYYY for last contact date where subjects are known to be alive
> mmYYYY for death date, data error and do not impute.
2. If both month and day are missing for death date or a death date is totally missing, do not impute and censor the subject survival time.

Appendix B. Wilson's Score Method with Continuity Correction in Calculating the 95% Confidence Intervals for Difference in 2 Independent Proportions

The following formula of interval estimation is extracted from [Newcombe 1998](#) paper:

Assuming

$X_i \stackrel{i.i.d.}{\sim} Bernoulli(\pi_1)$, where $i = 1, 2, \dots, m$.

$Y_j \stackrel{i.i.d.}{\sim} Bernoulli(\pi_2)$, where $j = 1, 2, \dots, n$.

$$\theta = \pi_1 - \pi_2$$

$$\hat{\pi}_1 = \sum_{i=1}^m x_i / m = a / m .$$

$$\hat{\pi}_2 = \sum_{j=1}^n y_j / n = b / n .$$

Then the $100(1 - \alpha)\%$ confidence interval for $\hat{\theta} = \hat{\pi}_1 - \hat{\pi}_2 = a / m - b / n$, with continuity correction is

$$\delta = z_{1-\alpha/2} \sqrt{\{l_1(1-l_1)/m + u_2(1-u_2)/n\}}$$

$$\varepsilon = z_{1-\alpha/2} \sqrt{\{u_1(1-u_1)/m + l_2(1-l_2)/n\}}$$

l_1 and u_1 delimit the interval $\{\pi_1 : |\pi_1 - a/m| - 1/(2m) \leq z_{1-\alpha/2} \sqrt{\pi_1(1-\pi_1)/m}\}$ and

l_2 and u_2 delimit the interval $\{\pi_2 : |\pi_2 - b/n| - 1/(2n) \leq z_{1-\alpha/2} \sqrt{\pi_2(1-\pi_2)/n}\}$.

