12.4 Investigator Responsibilities for Data Collection

The investigator is responsible for complying with the requirements for all assessments and data collection (including subjects not receiving protocol-required therapies) as stipulated in the protocol for each subject in the study. For subjects who withdraw prior to completion of all protocol-required visits and are unable or unwilling to continue the Schedule of Assessments (Table 2), the investigator can search publically available records [where permitted] to ascertain survival status. This ensures that the data set(s) produced as an outcome of the study is/are as comprehensive as possible.

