Time to treatment failure is calculated from first dosing until one or more of the following: (1) clinically relevant disease progression(PDr); (2) death from any cause; (3) non-clinically relevant disease progression (PDn) associated with a requirement for

alternative therapy as the reason for ending treatment or start of new anti-cancer therapy. Subjects without an event will be censored at their last evaluable tumor assessment.

This TTF definition is a modified definition of progression free survival (PFS). We do not penalize stopping treatment for CR or lack of injectable disease. In addition, the confirmation of PD is not required.

CCI

Treatment Period

Treatment period is defined as the period between the first date of IP administration in the study and 30 days after the last IP administration in the study.

Treatment-emergent Adverse Events

Treatment-emergent adverse events are defined as any adverse event occurring after initiation of the first dose of IP through 30 days after the last administration of IP in the study. Adverse events that occur on the same day as the first dose date of IP will be treated as treatment-emergent events unless indicated otherwise. (For example, if an event occurs on the same date as the first administration of talimogene laherparepvec and the check box indicating prior to the first dose of IP is checked, then the event will not be counted as a treatment-emergent AE).

Exposure-adjusted Subject Incidence

Exposure-adjusted subject incidence is defined as the number of subjects experiencing a specific event divided by their total subject-time at risk (summation of the time from first drug exposure to first event for subjects with at least one event or to death/end of study/30 days after last IP dose, whichever occurs first for subjects without the event).

Exposure-adjusted Event Rate

Exposure-adjusted event rates is defined as the number of occurrences that subjects experience of a specific event divided by their total subject-time at risk (summation over all subjects). Multiple occurrences of the same event for a subject are counted as events. For each subject, the time at risk will be defined as the start date of IP to death/end of study/30 days after last IP dose, whichever occurs first.

On-study Surgery/procedure

On study surgeries or procedures are defined as surgeries or procedures performed during the treatment period.

[figure not shown]
On-study Death

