11.3 Efficacy Endpoints

The efficacy analysis will be conducted using the safety analysis set unless otherwise specified. The ORR/ DRR/ Disease control rate will be estimated with the associated exact 95% CI ([Clopper and Pearson, 1934](#)). Wilson's score method with continuity correction ([Newcombe, 1998](#)) will be used to calculate an approximation of the exact CI for between-group differences in binary rates. Kaplan-Meier (K-M) estimates of landmarks (e.g., 1-, 2-, and 3-year rates) and quartiles for DOR, time to treatment failure and OS will be provided ([Kaplan and Meier, 1958](#)) . Greenwood's formula ([Kalbfleisch and Prentice, 1980](#)) for standard error will be used to calculate CIs for landmark K-M rates. CIs for K-M quartiles will be estimated ([Brookmeyer and Crowley, 1982](#)). In addition, changes in tumor burden for responders will also be summarized.

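### SAP Appendix A censors overall survival for subjects known to have died when the death date is year-only or missing, which biases the Kaplan-Meier estimate upward by a small amount

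*SAP*

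**What the plan says.** SAP Appendix A has two rules for incomplete death dates.

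- **Rule 1** applies when year and month are known and the day is missing. The death stays an event. If the subject was last known alive in the same month, it is dated the day after that contact; if in an earlier month, the instruction is to "set death date to the first day of the death month".
- **Rule 2** has two triggers and one consequence: "If both month and day are missing for death date", or where "a death date is totally missing, do not impute and censor the subject survival time".

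SAP Section 11.3 estimates OS and time to treatment failure (TTF) by Kaplan-Meier: landmark rates and "quartiles for DOR, time to treatment failure and OS will be provided". SAP Section 6 defines TTF separately. There "death from any cause" is an event, and "Subjects without an event will be censored at their last evaluable tumor assessment". The readable text does not say how TTF dates a death that has no usable date.

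Protocol Section 10.5 undertakes to pursue complete death dates and leaves imputation details to the SAP. Protocol Section 7.2.4 sets contacts every 12 weeks (± 28 days). For subjects who stop visits, Protocol Section 12.4 says "the investigator can search publically available records [where permitted] to ascertain survival status".

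**The concern.** Kaplan-Meier estimation assumes that censoring carries no information about the event. Under rule 2 the censoring is a consequence of the event: a subject can be censored this way only by having died. The observation lost is always a death, so the error runs in one direction.

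The rule also sits oddly in its own appendix. A death with a missing day is kept as an event at its earliest possible date. An adverse event whose start date is known only to the year is imputed. A death known only to the year loses its event status. No reason is given, although the anchor needed to date it, the last contact at which the subject was known alive, is already used in rule 1.

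OS is a secondary efficacy endpoint reported for a single arm, so there is no control arm in which the same error might cancel.

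**Working it through.** **No plan figure to reproduce.** The documents state no expected OS event count and no expected share of incomplete death dates. The size of the effect therefore rests on assumptions.

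**Inputs from the documents**
- 110 subjects (SAP Section 3.2).
- Enrolment over 17 months (Protocol Section 3.5.1).
- Follow-up to 24 months after the last enrolment, so the cut-off is month 17 + 24 = 41.
- Contact every 12 weeks.

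**Assumptions**
- Exponential survival with median 23.3 months, the phase 3 value in Protocol Section 2.2.
- Uniform enrolment.
- Censoring under rule 2 at the last contact before death, because the readable text gives no OS censoring date.

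**Direction.** Suppose n subjects are at risk at the last contact, j others die before this subject does, and nobody else is censored. Just after this death, the Kaplan-Meier factor is
- (n − j − 1)/n if the death is counted;
- (n − j − 1)/(n − 1) if it is censored at last contact.

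The second is larger, and the excess carries forward to later times.

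**Expected deaths.** λ = ln 2 / 23.3 = 0.02975 per month. Follow-up is uniform between 24 and 41 months, so the mean survival probability at cut-off is (e^(−24λ) − e^(−41λ))/(17λ) = (0.490 − 0.295)/0.506 = 0.384. Deaths = 110 × (1 − 0.384), about 68.

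**Size by number of deaths affected.** Simulated trials, last contact 0 to 12 weeks before death. With true dates, median OS is about 23.6 months and 24-month OS about 48.9%.

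| Deaths censored by rule 2 | Rise in 24-month OS | Rise in median OS |
|---|---|---|
| 1 | about 0.5 points | about 0.2 months |
| 3 | about 1.5 points | about 0.9 months |
| 5 | about 2.6 points | about 1.7 months |

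**Size by share f of deaths affected.** 3000 simulated trials per row, each with its own true-date estimate.

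| f | Mean deaths affected | Median OS, rule 2 vs true dates (months) | 24-month OS, rule 2 vs true dates |
|---|---|---|---|
| 1% | 0.7 | 23.9 vs 23.7 | 49.4% vs 49.1% |
| 2% | 1.3 | 23.9 vs 23.6 | 49.5% vs 48.9% |
| 5% | 3.4 | 24.6 vs 23.6 | 50.6% vs 48.9% |
| 10% | 6.8 | 26.0 vs 23.7 | 52.5% vs 49.0% |
| 20% | 13.6 | 29.0 vs 23.7 | 56.4% vs 49.1% |

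**Analytic check.** Dropping a share f of deaths scales the hazard by about (1 − f), so the median is about 23.3/(1 − f). This gives 23.5, 23.8, 24.5, 25.9 and 29.1 months, in line with the simulation.

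**Against sampling error.** Every subject has at least 24 months of potential follow-up in this scenario, so the standard error of 24-month OS is √(0.49 × 0.51/110) = 0.048, or 4.8 points. The 95% half-width is 1.96 × 4.8 = 9.4 points.

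**With the death kept as an event.** Dating it the day after last contact, across f = 1% to 20%, leaves the estimates within about 0.25 months and 0.3 points of the true-date values. If last contact is instead assumed to lie 6 to 18 months before death, 5 affected deaths shift 24-month OS by about +1.9 points under rule 2 and about −0.7 points when kept as events.

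**The case against.** The strongest reply is about frequency and materiality. Death dates are pursued, contact is 12-weekly, inconsistent data are queried before lock, and rule 1 already saves deaths with only the day missing. Protocol Section 12.4 says that records can be searched; it says nothing about how precise the dates found will be. The claim that such searches yield year-only dates is plausible but not documented. OS is descriptive, SAP Section 5 states that no formal hypothesis is tested, and the shifts for up to 5 deaths lie well inside the confidence interval. All of this stands. It limits the size of the problem but does not justify the rule, which governs exactly the cases where retrieval has failed.

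A second reply concerns the remedy. For a subject who stopped visits and was later found dead in public records, the last known-alive date may be long past, so the 12-week interval does not bound the dating error. That is correct. Even so, in the long-gap check the dated event is closer to the truth than the censored observation.

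Two stronger readings are tempting and the documents do not support them.

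- *These subjects are counted as survivors.* A censored subject leaves the risk set and is not carried forward alive. That description would fit only if censoring were placed at the data cut-off, which the readable text does not say.
- *Rule 2 also biases TTF upward.* Rule 2 speaks of survival time. The TTF definition makes any death an event and censors only subjects without one, so for TTF the readable text has a gap about dating, not a stated censoring rule. Subjects with an earlier TTF event are unaffected.

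Parts of SAP Sections 6 and 10.3 are blacked out. An OS definition, a censoring date or a sensitivity analysis may sit there, and their absence from the readable text is not held against the plan.

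**Conclusion.** Rule 2 is wrong as written for OS: it censors known deaths, the censoring is informative, and the bias was upward in every scenario run. The effect is small if such dates are few: at 2% of deaths or fewer, under about 0.4 months in the median and 1 point in the 24-month rate; at 5%, about 1 month and just under 2 points. It becomes material only at shares of incomplete dates that nothing in the documents suggests.

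These sizes rest on the assumed share of affected deaths, exponential survival at the phase 3 median, and censoring at last contact. The direction does not depend on the assumed share or the median. The primary endpoint, baseline CD8+ cell density against objective response, does not use death dates and is unaffected. The point merits correction because the rule is explicit and the change is nearly free, not because the trial's conclusions hang on it.

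**What to change.** Amend SAP Appendix A rule 2 so that a known death is always an OS event.

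1. **Year known, month and day missing:** date the death at the later of 1 January of that year and the day after the last known-alive date.
2. **Date wholly missing:** date it the day after the last known-alive date.
3. **Reporting:** list every death dated this way and give the number.
4. **Sensitivity analysis:** repeat the OS estimates with these deaths at the latest plausible date, meaning the end of the stated year or the date the death was learned of.
5. **TTF:** state that a death counting as a TTF event is dated in the same way.

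The cost is a few sentences in the SAP and one extra run of the OS analysis, with no new data collection. The downside is that imputed deaths are dated early: by up to the contact interval for subjects still followed, and possibly by many months for those who stopped visits. That biases OS slightly downward, but by less than rule 2 biases it upward, and the late-date analysis shows the range.
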